2.3.2 SAFETY RESULTS

A total of 12 patients were enrolled in this study. There were no SAEs reported.

In the 9 subjects analyzed on SCD treatment, no neutropenic events were reported. Mean WBC counts remained normal throughout treatment, with a mild decline noted upon initiation of therapy that was shown to rebound by day 7. No bleeding events were reported. Average platelet counts remained in the functional range (above 50,000) throughout treatment, with a mild decline noted upon initiation of therapy that was shown to plateau by day 4 to an average platelet count of 75,000. A summary of all adverse events (AEs) observed in the 9 subjects on SCD treatment is presented in **Table 2**. These events were not attributed to the

device by the investigator, as they commonly occur with CRRT treatment.

Table 2: Adverse event reporting – China Study – n=9 patients

Adverse Event (n=9 patients)	Number of Mild Severity Events	Number of Moderate Severity Events
Hypercalcemia	6	2
Thrombocytopenia	1	0
Hypocalcemia	0	1
Allergic Reaction	1	0
Hypophosphatemia	2	0
Hypernatremia	1	0

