6.2 CRRT PARAMETERS

6.2.1 CITRATE ANTICOAGULATION

Each participating clinical site will use their regional citrate anticoagulation protocol. The clinical site is responsible to achieve, and maintain a serum post filter ionized calcium level of <0.40 mmol/L throughout the entire observation period (day and night). The serum post filter ionized calcium level will be collected from the CRRT Circuit post SCD [REDACTED]

To alleviate the metabolic derangements associated with regional citrate based anticoagulation:

- a) *Alkalosis:* Patients with an arterial pH <7.40 at enrollment will initiate CRRT with solutions containing either 25 or 35 meq/L

of base as directed by local standard of care. During the study, if the patient's arterial pH increases to >7.45 OR the patient's serum bicarbonate increases to >35 meq/L, the CRRT solution will be changed to a base concentration of 25 meq/L, OR 0.9% NaCl will be added dialysis fluid to correct the alkalosis per local standard of care.

b) *Citrate lock:* If the patient develops citrate lock, as defined by a serum ionCa <0.95 mmol/L and a total serum Ca >12.5 meq/L, the citrate infusion will be discontinued OR the CRRT clearance will be increased by 50% per local standard of care, AND CRRT circuit Ca and patient Ca will be checked at least every one hour. For centers that stop citrate, once the patient ionCa is >1.0 mmol/L, the citrate will be restarted at 50% of the previous rate, and hourly ionCa pairs will be rechecked x 3 to ensure a stable patient ionCa >1 mmol/L and stable circuit ionCa <0.40 mmol/L.

Of importance the clinical plan is to monitor the perfusion circuit iCa levels at least q1h at the initiation of regional citrate anticoagulation (RCA) until a steady state iCa range is between 0.25 to 0.40 mmol/L. Once established, iCa levels both in the circuit and in the patient will be monitored q6h. If the iCa is outside the targeted range or alterations in citrate or calcium infusion rates are made, iCa levels are measured at least q1h until targeted ranges are once again achieved. Of importance, for efficacy of SCD treatment, iCa levels must be maintained in the recommended range at least 90% of the time, based on a sensitivity analysis showing that the mortality endpoint difference was lower with target iCa 80-85% of total treatment in clinical trial SCD-003.

The protocol example identified in **Appendix K** may be utilized.

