6.4 STUDY OBSERVATION PERIOD

The Study Observation Period begins when the patient starts treatment and will continue up to a maximum of 168 hours from the time of Observation Start. **Patient will begin the Observation Period before the patient has reached 12 hours on CRRT.** A patient may begin CRRT therapy and SCD treatment at the same time, which would also mark the beginning of the Study Observation Period.

This observation period has been broken into seven 24 hour time periods. It ends when the patient has reached 168 hours in the observation period or when the patient meets the termination criteria outlined in **Section 7.2** as determined by the Principal Investigator or Medical Team at the participating Clinical Site.

All tests are scheduled on a 24 hour cycle, or once a day, and can be scheduled to be drawn around each participating site's ICU blood drawing schedule, with the exception of any test that requires a specific draw frequency.

The following information will be obtained for patients enrolled during the study observation period on a daily basis unless otherwise specified:

- **Vital Signs/Physical Assessment**
 - Temperature
 - Blood Pressure , heart rate
 - Urine Output (previous 24 hours)
 - Net Fluid Balance (previous 24 hours)
- **Clinical Laboratory Tests**
 - CBC with differential – every 12 hours (+/- 4 hours)
 - BUN, Creatinine
 - Na, K, Cl, HCO₃, Ca, ionized Ca, Mg, PO₄
 - ALT, AST, Bilirubin, ALP, Total Protein, Albumin, Glucose
 - PT, PTT, INR
- **Respiratory**
 - Status – Ventilator support (yes/no; date of extubation)
 - If on Vent: FiO₂
 - If on Vent with an arterial line: Arterial Blood Gas
 - If on Vent without an arterial line: Arterial Blood Gas (if available)
- **Blood for Research**
 - Collect at hours 48, 96, 144, and end of study (+/- 4 hours). If study observation period ends prior to hour 168, collect at end of study observation period. Blood for biomarkers will be collected as close as possible to the time of SCD scheduled changes in the days required (+/- 4 hours) if practical.
 - Blood sample will be sent to an outside laboratory for testing of biomarkers

- **CRRT Parameters (Start at hour 0)**
 - Parameters include modality, blood flow rate, net fluid removal, dialysate or replacement solution flow rate, citrate infusion rate, calcium replacement rate.
 - System performance (circuit survival - event driven)
 - Post filter ionized calcium (+/- 1 hour)

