Therapy Initiation	Q 1 hr. until post filter iCa level <0.40 mmol/L; then Q 6hr.
After any Calcium or Citrate rate change	Q 1 hr. until post filter iCa level <0.40 mmol/L; then Q 6hr.
After any Interruption: Recirculation, Procedure, Restart	Q 1 hr. until post filter iCa level <0.40 mmol/L; then Q 6hr.

- **SCD Performance (Start at hour 0)**
 - SCD [REDACTED] performance (event driven)
 - SCD and SCD Blood Tubing Set Change every 24 hour (+/-4 hour)
- **Other (Event Driven)**
 - Acknowledgement (yes/no) to critical medications administered to the patient
 - Adverse Events
 - Diagnostic/Therapeutic Procedures
 - Microbiology/culture data

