APPENDIX F – SCD-PED-01 Study Schedule of Events

	Baseline	Hr 0-24	Hr 25-48	Hr 49-72	Hr 73-96	Hr 97-120	Hr 121-144	Hr 145-168	Therapy End
Vital Signs/Physical Assessment									
Temperature , Body Weight (baseline only)	X	X	X	X	X	X	X	X	
Blood Pressure (if no bp, MAP acceptable), Heart Rate	X	X	X	X	X	X	X	X	
PRISM II Score	X								
Physical Exam	X								
Urine Output (previous 24 hours)	X	X	X	X	X	X	X	X	
Net Fluid Balance (previous 24 hours)		X	X	X	X	X	X	X	
Sepsis	X								
ICU Percent Fluid Overload at CRRT Initiation	X								
Clinical Laboratory Testing									
CBC with differential	X	q12h	q12h	q12h	q12h	q12h	q12h	q12h	
BUN/Creatinine	X	X	X	X	X	X	X	X	
Na, K, Cl, HCO ₃ , Ca, Mg, PO ₄ , Ionized Calcium	X	X	X	X	X	X	X	X	
ALT, AST, Bilirubin, ALP, TP, Albumin, Glucose	X	X	X	X	X	X	X	X	
PT, PTT, INR	X	X	X	X	X	X	X	X	
Urinalysis (if urine is available)	X								
Respiratory									
Arterial Blood Gas (pH, PaO ₂ , PaCO ₂) (if on vent)*	X	X	X	X	X	X	X	X	
Ventilator Settings (FiO ₂)	X	X	X	X	X	X	X	X	
Blood For Research									
Blood for Biomarkers	X		X(hr/48)		X(hr/96)		X(hr/144)		X
Extracorporeal Device Parameters									
CRRT (Settings- Event Driven)	X (hour 0)	X	X	X	X	X	X	X	
Post Filter Ionized Calcium	X (hour 0)	q1h until <0.40mmol/L; then q6h	q6h	q6h	q6h	q6h	q6h	q6h	
CRRT Device and SCD Performance (Event Driven)		X	X	X	X	X	X	X	
SCD 24hr. Daily Change		X	X	X	X	X	X	X	
Other (Event-Driven)									
Adverse Events	X	X	X	X	X	X	X	X	X
Critical Medications, Blood products (yes/no) per Appendix J	X	X	X	X	X	X	X	X	X
Diagnosis/Therapeutic Procedures	X	X	X	X	X	X	X	X	X
Microbiology/culture data	X	X	X	X	X	X	X	X	

*Required only if the presence of an A-line; see **Section 6.3** and **Section 6.4** for details

APPENDIX G – SCD-PED-01 Study Schedule of Events: Follow-up Period**Day 1 - 5 or until ICU discharge (whichever occurs first unless otherwise specified)**

Measurement	Hour 0 - 24	Hours 25 – 120 ¹
Vital Signs/Physical Assessment		
Blood pressure, temperature, and heart rate	X	X
Physical Exam	X	
Urine Output (from previous 24 hours)	X	X
Net Fluid Balance – (from previous 24 hours)	X	X
Clinical Laboratory Tests		
CBC with differential	X	
BUN/Creatinine	X	
Na, K, Cl, HCO ₃ , Ca, Mg, PO ₄ , Ionized Calcium	X	
Respiratory:		
Arterial Blood Gas (pH, PaO ₂ , PaCO ₂)	X	
Ventilator Settings (FiO ₂)	X	X
Other(event driven)		
Renal Replacement Therapy status	X	X
Microbiology/Culture Data	X	X
Adverse Events	X	X
Serious Adverse Event	X	X
Antibacterial Medications (yes/no)	X	X

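### Patient ionized calcium is monitored every 6 hours but scheduled as study data only once a day, so the laboratory safety data will understate its extremes and the number of children ever out of range

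*Combined protocol and SAP*

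**What the plan says.** **Monitoring.** Section 6.2.1 states: "Once established, iCa levels both in the circuit and in the patient will be monitored q6h". If a level leaves its target, or a citrate or calcium infusion rate is changed, "iCa levels are measured at least q1h until targeted ranges are once again achieved". That sentence does not say whether it means the circuit, the patient or both.

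**Data schedule.** Section 6.4 says that the items in its list "will be obtained for patients enrolled during the study observation period on a daily basis unless otherwise specified". Ionized calcium is in the chemistry line ("Ca, ionized Ca, Mg") with no frequency attached, although the CBC in the same list is given a 12-hourly one. Post-filter iCa is listed separately under CRRT parameters with its own rule: "Q 1 hr. until post filter iCa level <0.40 mmol/L; then Q 6hr". Appendix F agrees. The chemistry row that contains ionized calcium has one mark per 24 h period, while the row "Post Filter Ionized Calcium" is hourly until below 0.40 mmol/L and then 6-hourly. Because the circuit value has its own row, I read the chemistry entry as the patient's value.

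**Exception.** Section 6.4 lets daily tests follow the local ICU draw times, "with the exception of any test that requires a specific draw frequency".

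**Other frequency.** The example citrate protocol in Appendix K checks patient and system iCa every 8 hours, not every 6.

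**Endpoints.** Section 3.1 makes safety the primary objective, and Section 3.2 names laboratory safety parameters among the safety measures.

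**The concern.** The circuit value shows whether the device is running under the intended conditions. The patient value shows whether the child is exposed to low or high systemic calcium, which the protocol itself treats as a foreseeable effect: Section 6.2.1 deals with citrate lock, and Section 9.4 lists hypo- and hypercalcemia as anticipated. The plan gives the circuit value a data schedule that matches its monitoring and gives the patient value one that does not.

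If the schedule is followed as written, the laboratory safety tables will rest on one patient iCa per day, at a time that may be set by the ICU's routine draws. Up to 30 children will be enrolled, so there is little other information on how often, how far and for how long systemic calcium leaves its range.

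One earlier study makes this relevant. Section 2.3.2 introduces Table 2 with the words "A summary of all adverse events (AEs) observed in the 9 subjects on SCD treatment is presented in", and most events in that table are calcium events.

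**Working it through.** The plan states no figure for this point, so there is none to reproduce. The check counts scheduled values and asks what a daily value can detect.

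**1. Values with and without a slot**

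Inputs: maximum observation period 168 h (Section 6.4); patient iCa every 6 h (Section 6.2.1) or every 8 h (Appendix K example); data once per 24 h (Section 6.4, Appendix F); 72 h minimum treatment for the final outcome analysis (Section 11).

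| Course | Monitored | Scheduled as data | No slot |
|---|---|---|---|
| 168 h, 6-hourly | 168/6 = 28 | 168/24 = 7 | 21/28 = 75% |
| 168 h, 8-hourly | 168/8 = 21 | 7 | 14/21 = 67% |
| 72 h, 6-hourly | 72/6 = 12 | 72/24 = 3 | 9/12 = 75% |

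Triggered hourly re-checks of the patient would raise the share without a slot.

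**2. Which summaries are affected**

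If the 7 daily values are a subset of the 28, their minimum cannot be below the true minimum of the 28, nor their maximum above the true maximum. A patient can be out of range among the 28 and never among the 7, but not the reverse. Extremes and ever-out-of-range counts can therefore only be equal or understated.

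The proportion of values out of range behaves differently. If the daily draw falls at random relative to excursions, that proportion is estimated without bias, only less precisely.

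**3. Excursions a daily value would miss**

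Assume an excursion of D hours starting at a uniformly random time. It meets a daily draw with probability min(D/24, 1) and a 6-hourly draw with probability min(D/6, 1). Among excursions seen at 6-hourly draws, the share missed by the daily value is 1 − min(D/24, 1)/min(D/6, 1).

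| D (h) | Daily | 6-hourly | Missed by daily |
|---|---|---|---|
| 3 | 12.5% | 50% | 75% |
| 6 | 25% | 100% | 75% |
| 9 | 37.5% | 100% | 62.5% |
| 12 | 50% | 100% | 50% |
| 18 | 75% | 100% | 25% |
| 24 | 100% | 100% | 0% |

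More than half are missed only when D is below 12 h. The documents give no durations, so D is an assumption. The hourly re-check rule makes short excursions plausible but does not establish them.

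**4. Prior calcium events**

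Table 2: hypercalcemia 6 + 2 = 8; hypocalcemia 1; all events 8 + 1 + 1 + 1 + 2 + 1 = 14. Calcium events are 9/14 = 64%, in 9 patients, and the investigator did not attribute them to the device. Table 1 (ESRD study) has 19 + 13 = 32 events and no calcium term. Table 3 (ARF-002) has 199 events, not listed by term.

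**The case against.** **The text may already allow 6-hourly recording.** Section 6.4 exempts tests with their own draw frequency, and Section 6.2.1 gives patient iCa one. The case report form is not in the documents. So a reader who infers that these values are lost goes further than the text allows. What stands is that actual capture cannot be confirmed. But the exception concerns when blood is drawn, and Appendix F still shows one chemistry entry per 24 h. If sites can read it either way, capture may differ by site.

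**Adverse event reporting is a second route.** Section 9.1 names hypercalcemia and hypocalcemia, Section 9.7 asks for expected ICU events that meet the definitions, and 6 of the 9 calcium events in Table 2 were mild. This has force: clinically significant excursions may well be reported. But a laboratory value becomes an adverse event only if judged clinically significant, and an event report does not replace serial values showing depth, duration and frequency.

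**Infusion rates leave a trace.** Citrate and calcium rates are collected, and in the Appendix K example the calcium rate is adjusted to patient iCa. That shows a correction was made, not the level that prompted it.

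**Calcium disturbance might be taken as the commonest SCD adverse event.** Table 2 shows this for one 9-patient study only. Table 1 has no calcium event and Table 3 gives no terms. In SCD-003, serious metabolism and nutrition events occurred in 2/69 with SCD and 2/63 with control (Table 4), but non-serious events are not shown. No programme-wide ranking follows.

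**Conclusion.** The mismatch is real and worth correcting. As written, 75% of the 6-hourly patient iCa values (67% under the 8-hourly example) have no explicit data slot, while circuit iCa has a matching one. The laboratory safety data will therefore understate the extremes of patient iCa and the number of patients ever out of range. This rests on two readings: that the chemistry-line ionized calcium is the patient's, and that sites follow Section 6.4 and Appendix F literally.

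Two stronger statements are not supported. That most excursions go unseen holds only for those shorter than about 12 h with random timing, and no durations are given. That every out-of-range rate will be too low is wrong, because the proportion of time or values out of range is not biased by random daily sampling.

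This should be changed before data collection. It does not invalidate the design.

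**What to change.** - **Schedule.** In Section 6.4 and Appendix F, add a separate row for patient ionized calcium. Record every value already obtained under Section 6.2.1, or at least the minimum and maximum in each 24 h period. Keep it apart from the post-filter row: post-filter iCa is sampled from the circuit, and at initiation Section 6.2.1 asks for hourly checks of the circuit only, so a merged row could be read as requiring extra patient samples. State that no draws are added.
- **Flag.** Mark scheduled 6-hourly values separately from triggered re-checks. Re-checks cluster around excursions, so pooling them would bias a raw proportion out of range upward.
- **Analysis.** Report each patient's lowest and highest patient iCa and whether it was ever out of range. Compute any proportion out of range from scheduled values only, or time-weighted. The sponsor should prespecify the reporting range: 1.1 to 1.3 mmol/L appears only in the Appendix K example, and Section 6.2.1 uses 0.95 and 1.0 mmol/L for citrate lock.
- **Reconcile.** Section 6.2.1 (every 6 hours) and Appendix K (every 8 hours) must be brought into agreement. Which is right is for the sponsor to decide.

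Cost: 28 − 7 = 21 more entries per patient over 7 days, at most 30 × 21 = 630 for the trial, plus any re-checks. The reported rate of calcium abnormalities may rise.

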6.5 STUDY FOLLOW UP PERIOD

6.5.1 POST END OF STUDY TREATMENT PERIOD

This Study Follow Up period has been broken into five 24 hour time periods. It starts when the patient has reached 168 hours in the observation period or when the patient meets the termination criteria outlined in **Section 7.2**. It ends at 120 hours or ICU discharge, whichever comes first. Record the following data daily in the Study Follow-up Period unless otherwise noted:

- **Vital Signs/Physical Assessment**
 - Blood pressure, heart rate, temperature
 - Physical Exam (first 24 hours only)
 - Urine Output (from previous 24 hours)
 - Net fluid balance (from previous 24 hours)
- **Clinical Laboratory Tests (first 24 hours only)**
 - CBC with differential
 - BUN, Creatinine
 - Na, K, Cl, HCO₃, Ca, Mg, Ionized Ca, PO₄

- **Respiratory**
 - Status – Ventilator support (yes/no)
 - If on Vent: FiO₂
 - If on Vent with an arterial line: Arterial Blood Gas(first 24 hours only)
 - If on Vent without an arterial line: Arterial Blood Gas (if available, first 24 hours only)
- **Renal Replacement Therapy status**
 - RRT status
- **Other (Event Driven)**
 - Microbiology/culture data
 - Adverse Events
 - Acknowledgement (yes/no) to antibacterial agents administered to the patient.

6.5.2 DAY 28 POST ENROLLMENT

This visit may be done via telephone call or office visit. Please record the following information on day 28 (+7 days) following enrollment:

- Presence / date of mechanical ventilation (since last visit)
- Presence / date of renal replacement therapy (since last visit)
- Serious Adverse events (since last visit)
- Serum creatinine (if an office visit takes place)

6.5.3 DAY 60 POST ENROLLMENT

This visit may be done via telephone call or office visit. Please record the following information on day 60 (+7 days) following enrollment:

- Presence / dates of mechanical ventilation (since last visit)
- Presence / dates of renal replacement therapy (since last visit)
- ICU discharge date
- Hospital discharge date
- Serious Adverse events (since last visit)
- Serum creatinine (if an office visit takes place)

7. TREATMENT INTERRUPTIONS – DISCONTINUATION CRITERIA

7.1. TREATMENT INTERRUPTION CRITERIA

The SCD is to be used continuously along with CRRT and changed every 24 hours and at any time the circuit exhibits significant clotting that impairs the functionality of the circuit.

In the event that a procedure is needed (e.g. CT-Scan, MRI), SCD treatment may be interrupted for a maximum of 12 hours (cumulative) per 24 hour period for these indications. In the event a patient needs to initiate ECMO in the middle of the SCD course, SCD treatment may be interrupted for up to 24 consecutive hours. Cumulative interruption of greater than 12 hours (or 24 hours for ECMO) will trigger the end of Observation Period and immediate initiation of the Follow-up period. These patients will not be removed from the study unless consent is withdrawn.

7.2. TREATMENT DISCONTINUATION CRITERIA

Patients may be withdrawn from therapy prior to hour 168 for a variety of reasons. When therapy is discontinued prior to hour 168, the follow-up period will immediately begin and data will continue to be collected per protocol.

The Principal Investigator will assign a primary reason for therapy termination utilizing the categories listed in 7.3 and 7.4 below, and if appropriate, one or more subcategories.

7.3. CLINICAL CRITERIA:

1. Improvement in Clinical Status

If a patient's condition improves (e.g. renal condition has improved to the extent that CRRT can be discontinued or hemodynamic status has improved so that the dialysis modality can be changed from CRRT to IHD) treatment may be discontinued before the 168 hour treatment period. The decision to discontinue treatment based upon improvement in clinical status will be made by the Principal Investigator.

2. CRRT related medical events

Such as persistent leukopenia, neutropenia or thrombocytopenia based upon PI's clinical assessment.

3. SCD related medical events

Such as persistent leukopenia, neutropenia or thrombocytopenia based upon PI's clinical assessment of relationship to SCD.

4. CRRT Failure/Malfunction

Failure of the CRRT device and/or circuit, including inability to maintain vascular access that requires treatment to be discontinued prior to hour 168 of therapy.

5. SCD Failure/Malfunction

Any failure of the SCD █ that requires treatment to be discontinued prior to hour 168 of therapy e.g. clotting or evidence of leakage in the SCD █ or inability to maintain a patent circuit.

6. Death**7. Withdrawal of life support****8. Concomitant Medical Conditions**

Need for medical, surgical or diagnostic procedures that necessitate discontinuation of SCD treatment for longer than the allowable 12 hours per 24 hour period.

9. Regional Citrate Anticoagulation Intolerance

All patients must be able to tolerate and achieve satisfactory regional citrate anticoagulation. Tolerance of regional citrate anticoagulation is defined as achieving:

- Two (2) consecutive circuit ionized calcium levels of < 0.40 mmol/L (or < 1.6 mg/dL),
- At least 30 minutes apart, and
- Within the first 12 hours of CRRT initiation.

If unable to achieve the specific circuit ionized calcium levels within the time frame above, treatment with the SCD must be discontinued. The patient will progress on to the post-SCD follow up period, unless the patient and/or legal guardian withdraws consent for the study.

10. Other

Any other reason that the Principal Investigator deems appropriate for discontinuation from the Study Observation period must be documented.

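### Section 7.3 item 9 needs two in-range circuit iCa values by CRRT hour 12, but the 6.4 table and Appendix F end hourly draws after one: a conflict in the text with a minor risk of stopping SCD in an in-range child

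*Combined protocol and SAP*

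**What the plan says.** **The stop rule (7.3 item 9).** Tolerance of regional citrate means "Two (2) consecutive circuit ionized calcium levels of < 0.40 mmol/L", separated by 30 minutes or more, and obtained "Within the first 12 hours of CRRT initiation". The consequence is mandatory: "If unable to achieve the specific circuit ionized calcium levels within the time frame above, treatment with the SCD must be discontinued". Follow-up then continues unless consent is withdrawn. Section 7.2 leaves the label to the site: "The Principal Investigator will assign a primary reason for therapy termination utilizing the categories listed in 7.3 and 7.4 below".

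**The sampling schedule (6.4 table).** All three rows carry the same instruction: "Q 1 hr. until post filter iCa level <0.40 mmol/L; then Q 6hr". The rows cover therapy initiation, "After any Calcium or Citrate rate change" and "After any Interruption: Recirculation, Procedure, Restart". Draws have a window of one hour either way. The Hr 0-24 cell of Appendix F gives the same single-value rule, and Appendix F also lists an hour-0 reading.

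**The clocks.** Item 9 counts from the start of CRRT. Study readings count from the start of the Observation Period, that is, of SCD treatment, which may be any time before CRRT hour 12 (6.4).

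**Citrate management (6.2.1).** This section is broader. It keeps circuit draws at least hourly until a steady state between 0.25 and 0.40 mmol/L, without saying how many readings show that. After an out-of-range value or a rate change, it keeps them hourly until target ranges are regained. It specifies sampling after the SCD.

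**The concern.** The stop rule needs a pair of values. The operational schedule asks for one and then waits about six hours. A site that follows the table and item 9 to the letter could reach CRRT hour 12 with a single reading, in range, and no pair. It would then face an instruction to stop SCD in a child whose circuit calcium is where the protocol wants it.

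A slow response to citrate is not required. Because the item 9 clock may already have run for hours when SCD starts, a late SCD start is enough.

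What is at stake is limited. SCD would be withdrawn for a reason unrelated to tolerance and recorded as citrate intolerance. The child would have had at most 12 h of SCD, below the 72 h that section 11 requires for the final outcome analysis. Sites could also handle the same situation differently.

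**Working it through.** The plan states no figure on this point, so there is none to reproduce. The check is timing arithmetic.

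**Inputs**
- Deadline: 12 h from CRRT start (7.3 item 9).
- Minimum spacing of the pair: 0.5 h (7.3 item 9).
- Gap to the next draw after one in-range value: 6 h, or 5 to 7 h with the one-hour window (6.4 table; Appendix F).
- SCD start: CRRT hour *t*, with *t* < 12 (6.4).
- Minimum exposure for the final outcome analysis: 72 h (section 11).

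**Step 1. Current schedule.** Let *f* be the CRRT hour of the first in-range reading. A second scheduled reading arrives in time if *f* + 6 ≤ 12, so *f* ≤ 6. With a 7 h gap, *f* ≤ 5; with a 5 h gap, *f* ≤ 7.

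| First in range (CRRT hour) | Next draw now (window) | By hour 12? | Next draw, two-value wording |
|---|---|---|---|
| 3 | 9 (8 to 10) | yes | 4 |
| 5 | 11 (10 to 12) | yes | 6 |
| 6 | 12 (11 to 13) | just, if on time | 7 |
| 7 | 13 (12 to 14) | only if an hour early | 8 |
| 9 | 15 (14 to 16) | no | 10 |
| 11 | 17 (16 to 18) | no | 12 |

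**Step 2. What can still supply the second value.**
- A rate change or interruption at CRRT hour *r*, after the first in-range reading, restarts hourly draws. The next draw is at *r* + 1 ≤ 12, so *r* ≤ 11 (10 to 12 with the window), provided that it falls 0.5 h or more after *f*.
- If the hour-0 reading is in range and the first hourly draw still follows, *t* + 1 ≤ 12, so a pair exists for SCD starts up to CRRT hour 11.
- The steady-state wording in 6.2.1, circuit readings before SCD start, or an unscheduled repeat could each supply it. No number can be put on these.

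**Step 3. Two-value wording.** *f* + 1 ≤ 12 gives *f* ≤ 11. A draw one hour late gives *f* + 2 ≤ 12, so *f* ≤ 10. A 30-minute repeat gives *f* + 0.5 ≤ 12, so *f* ≤ 11.5. The gain over Step 1 is 11 − 6 = 5 h.

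**Step 4. Exposure if stopped at CRRT hour 12.** 12 − *t* ≤ 12 h, against the 72 h required.

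**The case against.** The strongest reply is that the 6.4 table is shorthand and that 6.2.1 governs citrate management. One value cannot show a steady state, so a site following 6.2.1 would keep drawing hourly and would obtain the pair. This carries real weight. It does not remove the conflict, because steady state is undefined and the table and Appendix F, which bedside staff work from, give a different rule.

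Other parts of the reply also stand:
- **Rate changes.** A reader might infer from the 6.4 row that the change which brought the child into range cannot help, since that row also stops at one value. This does not hold under 6.2.1. Draws there stay hourly until target ranges are regained, the circuit range has a lower limit of 0.25, and the preceding sentence speaks of circuit and patient levels together. Hourly draws can therefore continue past the first circuit value below 0.40.
- **Appendix K.** A reader might infer that a child inside the nurse-call limits has no further rate change. But the example lowers calcium chloride by 10% at patient iCa 1.3 to 1.5 mmol/L, while the upper call limit is 1.5. It also asks for a system check one hour after any change.
- **Wording of the stop rule.** It is triggered by being unable to achieve the levels. An unmeasured value need not count as inability, and nothing bars a repeat draw.
- **Earlier readings.** A clock that runs from CRRT start makes good sense if circuit readings before SCD count. Against this, 6.2.1 specifies sampling after the SCD, and item 9 is silent.

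**Conclusion.** The conflict is in the text. Item 9 requires two values, while the 6.4 table and the Appendix F Hr 0-24 cell schedule one before the six-hourly interval. On those schedules the cut-off is about CRRT hour 6 (5 to 7).

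A reader might infer that every child first in range after hour 6 would lose SCD. The documents do not support that. A wrongful stop needs several things at once: no qualifying rate change, interruption, hour-0 or earlier reading; no repeat draw; a site that takes one value as steady state; and an investigator who treats a missing reading as intolerance. That combination should be uncommon. Its frequency is unknown, because the documents give no distribution of SCD start times or of time to the first in-range reading.

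The point is minor. This is a pilot whose primary objective is safety, and follow-up continues after SCD stops. The likelier effect is inconsistent handling between sites. Confidence is high for the mismatch and the cut-off, but not for any claim that children would be stopped wrongly.

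**What to change.** In the 6.4 table and the Hr 0-24 cell of Appendix F, until item 9 has been met, write: *q1h until two consecutive values <0.40 mmol/L at least 30 minutes apart, then q6h*. Once item 9 has been met, the present single-value wording can stay for rate changes and interruptions.

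The cost is one phrase in three table rows and one cell, and about one extra draw per patient from a circuit already being sampled. The 12 h clock does not change.

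Two limits should be kept in view. The new wording does not define steady state in 6.2.1: that range is 0.25 to 0.40 mmol/L, and two readings of 0.15 would satisfy item 9 without lying in it. A child first in range after about CRRT hour 11 (10 to 11.5) would still have no second reading in time.

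Optionally, the sponsor could state in item 9 whether circuit readings taken on citrate before SCD start count. Because 6.2.1 specifies sampling after the SCD, that is for the sponsor to decide.
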